- Recruitment will start initially with the first 106 identified through the excel program for the two groups and will continue until 106 participants have been recruited into both arms.

Rationale for Study Design TSRAC QUESTION 1 (Response)

- According to the NHMRC levels of evidence, a RCT is level 2 evidence and a systematic review of RCTs is level 1 evidence. Program evaluation is not a research method. Rather, program evaluation is conducted using a range of different research methods that are adapted to the task of evaluation depending on the program and the circumstances of its implementation. As this study is an intervention study that examines the effectiveness of an obesity model of care in patients with type 2 diabetes, the higher level of evidence is a RCT and is the study design that the research team wishes to use.
- Initially, all patients will be provided with quality evidenced based care at all times for diabetes and obesity; this form of care for both groups will not alter.
- The potential difficulty for team members to provide services differently depending on whether a client is in the control or intervention group has been addressed by separating participants from the control and intervention group into different clinics. The control group will be seen in the usual diabetes clinic with no particular focus on obesity management and/or the many factors that impact on obesity.
- At differing times a patient in the control group may have an assessment taken ie DASS due to an issue isolated in the course of the clinic however; this is not common but will be accounted for post-hoc in our data analysis.
- The intervention group will have onsite on the day of the clinic a more extensive multidisciplinary team that will be involved in assessment and treatment; unlike the control group clinic.
- Services and treatment will differ due to these assessments and measurement of other markers eg psychometric and pain scales that will prompt differing care and treatment plans.

Methodology

TSRAC QUESTION 2 and 3 (Response)

Randomisation

- All patients referred to the Diabetes Centre are listed in the services clinical software program DiaBASE.
- The list of potential participants was drawn from this program (that is inclusive of all patients as at 10/9/2014)

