- Once those that met the exclusion criteria were removed this list of potential participants (359) has been ranked from highest to lowest – at this stage they have been allocated a study number of 1 to 359, 1 being the participant with the highest BMI and 359 with the lowest.
- Numbers have been assigned for the two arms of the study from the computer random number generated via excel.
- According to numbers allocated to the potential participant list these are then assigned to the two arms of the study (intervention and control).
- This will occur once ethic approval has been gained and prior to allocation to clinics
- Once case identified and consent gained participants will be recruited from pre-existing clinics
- Outcome measures will be collected at baseline and at appropriate intervals at 6, 12, 18 months and post intervention at 12 and 24 months.

Study Intervention

- Outcome measures including quantitative and qualitative data **not** usually collected as part of a diabetes clinic will be collected to support the development of individualised plans of care:
 - Absolute cardiovascular disease risk

- Patient Health Questionnaire (PHQ-9) [Depression] and Generalised Anxiety Disorder Assessment (GAD-7) [Anxiety] and SF-36 Quality of Life scaling, Assessment and Quality of Life (AQoL), Work Productivity and Activity Impairment (WPAI)
- McCaffery Pain assessment scale and Physical function status
- Edmonton obesity staging
- Sleepiness Scale
- Metabolic clinical markers (HbA1c, lipids, leptin, ketone, vitamin D, B12, TFTs, LFTs, ACR, eGFR)
- Physical measurements (eg BMI, girth, blood pressure)
- Assessment is undertaken initially on the same day by the physiotherapist in terms of pain management and ability to increase physical activity – these assessments are provided to the endocrinologist and Dietitian at which time a treatment plan is developed in partnership with the client by the multidisciplinary team including:
 - Referral to other health professionals and/or assessments (eg Snore Aust, pain clinic)
 - According to scores from psychometric, physical functioning and/or pain scales participants will be divided into groups A, B or C and referred on for either a once off individual consultation, a series of individual consultations or a group program with relevant AHP.
 - Regular psychology review for CBT and other relevant therapies (according to PHQ-9 and GAD-7)
 - Resistance and hydrotherapy training
 - Medical nutritional therapy

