This study looks at the effects of care that is tailored to obesity. Patients invited to the study will be told about what they will need to do if they decide to be involved. They will be asked to provide written consent before being placed at random to the treatment group or normal care. Participants in the control group will receive routine care as part of the normal Adult Diabetes Clinic. Participants in the intervention group will complete a number of hand written assessments about sleep, pain, stress and/or how they have been feeling. Some measurements of body shape will be taken as well as some blood tests each 6 months. Some of these are routine tests for normal care and others are specific to the study. All participants will attend the service each 3 months – that is 4 times per year – these visits may last 30 to 90 minutes. At these times they may see other health professionals such as a physiotherapist, psychologist or dietitian – this will be on an individual basis at first and then may be in a group format. The group programs will involve learning about ways to stop the cycle of obesity and/or some physical activity. If no weight loss is achieved a dose of Orlistat will be suggested for a 3 month period. The participants will be contacted by the research assistant to arrange a time for their follow-up visits and to see how they are doing overall. If suitable and willing the participants may be referred to see a surgeon to discuss other options.

Nature of Existing Relationships between Potential Participants/Research team and Voluntary Consent

A majority of the participants will have had a past and/or current relationship with a number of the health professionals involved in the research study group. Potential participants will be clearly informed that their relationship with any of the investigations or staff involved in their medical care will not be influenced by their choice to participate or not to participate.

Potential participants will be assured that the decision to participate is voluntary and will have no influence on their relationship with medical or allied health professional staff, the research team or the THO-North West.

Impact of the research on the Relationship between Participants and the Researcher

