Our study aims to look at the effects of care that is tailored specifically to obesity. The study involves complete several hand written assessments about sleep, pain, stress and/or how they have been feeling. If you need assistance with this we will provide this. Also some measurements of your body as well as some blood tests each 6 months. Some of these are routine tests for normal care and others are specific to the study. You will visit the clinic each 3 months – that is 4 times per year – these visits may last 30 to 90 minutes. At these times you will see other health professionals such as a physiotherapist, psychologist or dietitian – this will be on an individual basis at first and then may be in a group format. The group programs will involve learning about ways to stop the cycle of obesity and/or some physical activity. You can discuss these options with the staff member at the time – you will not be forced to go into any specific treatment. If no weight loss is achieved a dose of Orlistat will be suggested for a 3 month period. If after 12 months weight loss is still low and you are interested, you may be referred to a surgeon to discuss other options."

Given participants are existing patients of the service and will continue to be review as part of routine care at the Diabetes Centre, at their 24 month collection point (intervention and control) they will be invited to continue with a collection of indicated markers at 6 and 12 months post intervention. If at this last visit they indicate that they are happy for this to occur this verbal consent will be added to the spreadsheet used to collect the project data – ie consent given: yes and date.

Would knowledge of recruitment, participation or exclusion Expose the Person to Disadvantage or Risk

No

Seeking Consent

- Potential participants are identified through records of patients with BMI >30 via DiaBASE program (clinical software program) in order of last review
- Participants will be screened for eligibility by the Research Assistant after this list is generated
- We will use a random number generator to assign patients to groups
- After an initial notification that the individual has been identified as a potential participant for the study on their next appointment letter the Research Assistant will invite the potential participant to be involved in the study
- The research assistant will have had previous training in seeking informed consent

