- Informed Consent will be gained by the Research Assistant/ Case Manager in written form
- Participant information will be forward to research team immediately and patient booked into next available AMOS Clinic
- As outlined previously, participation is voluntary. Prior to entry into the study potential participants will be informed of their ability to withdraw at any time, without giving a reason should they wish – the intervention and resources being tested in the study will no longer be made available to withdrawn participants. Withdrawn participants will re-enter the normal Adult Diabetes Clinic.
- There will be no payments made to participants involved in the study

Confidentiality and Privacy

Participant names, their details and data will be kept on a password protected database and will only be linked to a study identification number for this research. Patient information will initially be entered into DiaBASE (a clinical software program that is password protected) on computers that are also password protected. On transportation of data from DiaBASE to excel format only THCI numbers will be included initially – to track any missing data initially – this will then be removed at the study identification number allocated.

At this point there is no patient identifiers. All data will be entered into a computer that is password protected, stored in a locked office of the investigator and maintained for a minimum of 3 years after completion of the study.

Safety Considerations

Expected Benefits to the Wider Community

- The development of an evidenced based tiered model for individualised interdisciplinary care to support obesity management and reduce comorbidity risk.
- Improved patient outcomes which in turn reduce health costs to the community
- Improve best practice in the management of obesity
- Will provide information to support change in service delivery and policy development
- Assessment of process and impact outcomes to substantiate and drive clinical and policy change supportive of a multidisciplinary systematic approach for patients living with obesity.
- The development of a model of care that supports the self and medical management of obesity; taking into account the experience and the context for the person as well as their physical measurements and indicators.
- The development of a framework for improved obesity management for rural Tasmanians with diabetes and obesity.

Expected Benefits to Participants

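### Listed patients are assigned to arms before they are invited and give written consent, with no concealment described, although other sections put consent first

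*Protocol*

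**What the plan says.** The protocol describes the order of events in four places.

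- **Methodology, Randomisation.** Exclusions come first: "Once those that met the exclusion criteria were removed this list of potential participants (359) has been ranked from highest to lowest". The remaining patients carry numbers 1 to 359. Then: "According to numbers allocated to the potential participant list these are then assigned to the two arms of the study (intervention and control". The timing is tied to ethics approval and clinic allocation, not to consent: "This will occur once ethic approval has been gained and prior to allocation to clinics". Consent appears only in the bullet after that.
- **Study Design.** One bullet has participants recruited, listed by BMI and afterwards randomised. The next starts from the first 106 identified by the Excel program for the two groups and "will continue until 106 participants have been recruited into both arms".
- **Seeking Consent.** The bullets run: list drawn, eligibility screening, random assignment, notice in the appointment letter, invitation, written consent, booking. On screening: "Participants will be screened for eligibility by the Research Assistant after this list is generated". The step after consent is: "Participant information will be forward to research team immediately and patient booked into next available AMOS Clinic". No randomisation step follows consent.
- **Lay Description of Participation.** "They will be asked to provide written consent before being placed at random to the treatment group or normal care".

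The same Research Assistant/Case Manager screens, invites and takes consent. The personnel section also gives this role the task of seeing that planned care is delivered, and of collecting data. No section mentions allocation concealment.

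**The concern.** Randomisation protects a comparison only if the decision to enter a patient is made without knowledge of the arm. If the arm is fixed on a list first, the recruiter may approach, follow up or encourage patients differently according to where they are due to go. The trial is open, and the two arms differ greatly in what they offer, so there is a motive for this even in good faith.

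Selection of this kind would act on traits such as motivation or expected adherence, which plausibly affect weight and HbA1c, the two primary outcomes. The planned adjustment covers age, pre-existing diabetes, socio-economic status and ethnicity, and does not reach those traits. The problem arises at enrolment, so a statistical analysis plan cannot repair it.

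The protocol also tells patients one order and instructs staff in another, so the site cannot follow both.

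**Working it through.** **1. Order of steps, side by side**

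| Section | Order | Assignment relative to consent |
|---|---|---|
| Randomisation | exclusions removed, numbered, assigned, consent | before |
| Study Design, recruitment bullet | groups identified, recruited to 106 in each | before |
| Seeking Consent | list, screened, assigned, letter, invitation, consent, booking | before |
| Study Design, assignment bullet | recruited, listed, assigned | after |
| Lay Description | written consent, then placed at random | after |

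Three descriptions put assignment first and two put it last. The three are the operational ones. Recruiting until each of two groups holds 106 makes sense only if a patient's group is set before the approach.

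**2. The planned sample size**

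Inputs from Sample Size: d = 0.5, power 0.95, significance level 0.05. Two-sided testing is assumed because sidedness is not stated.

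- Normal approximation: n per arm = 2 × (1.960 + 1.645)² / 0.5² = 104, or 208 in total.
- Exact noncentral t: 105 per arm, or 210 in total.
- Power at 106 per arm is 0.952 (t) or 0.954 (normal).

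The stated 212 is reproduced, and the order of consent and assignment does not affect it.

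**3. Possible loss between assignment and entry**

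Assume the whole list of 359 is assigned, split evenly.

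- 359 − 212 = 147, and 147 / 359 = 40.9%.
- Minimum uptake to fill both arms: 212 / 359 = 59.1%. Per arm it is 106/180 = 58.9% or 106/179 = 59.2%.

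The 147 is a ceiling. Patients never approached because their arm is already full are not selected through consent.

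**4. What selection could do (illustration only)**

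The protocol gives no figure for how consent relates to prognosis, so r below is assumed. Let willingness to consent be normally distributed, with uptake p, and let its correlation with outcome be larger by r in one arm than in the other. The difference in means created by selection is r × φ(z)/p, in SD units. At p = 0.5905, φ(z)/p = 0.658. With 106 per arm, the test statistic shifts by bias × √(106/2) = bias × √53, and the type I error is P(|Z + bias × √53| > 1.96).

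| Assumed r | Bias (SD) | Share of d = 0.5 | Type I error |
|---|---|---|---|
| 0.1 | 0.066 | 13% | about 8% |
| 0.2 | 0.132 | 26% | about 16% |
| 0.3 | 0.197 | 39% | about 30% |

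These use the minimum uptake. With less refusal the effect shrinks: if 10% refuse in one arm only and the correlation is 0.2, the bias is 0.039 SD and the type I error 5.9%. If 30% refuse in one arm and the correlation is 0.4, the figures are 0.199 SD and 30%.

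**The case against.** Several stronger readings are tempting, and the protocol does not support them.

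- **Assignment precedes eligibility screening.** A reader might infer this from the use of a clinic list. However, Randomisation removes excluded patients before numbering, and Seeking Consent lists screening before the random-number step.
- **The recruiter knows the arm.** No section says so. It is a fair inference from recruiting into pre-filled groups, but the documented fact is only that no concealment is described. There is also a partial safeguard: researchers who treat a patient are kept from raising the study with that patient.
- **The trial compares people who agreed to AMOS with people who agreed to be controls.** The protocol gives one letter and one telephone script, with no version for each arm. Self-selection by patients according to arm is therefore not shown, and recruiter behaviour is the clearer route. The script does not mention chance or a control group, though, and that needs correcting in its own right.
- **The list is ordered in two incompatible ways.** Seeking Consent retrieves records by date of last review ("Potential participants are identified through records of patients with BMI >30 via DiaBASE program (clinical software program) in order of last review") and Randomisation ranks by BMI. Retrieval followed by ranking reconciles the two.
- **Every consenting patient goes to AMOS.** The booking bullet reads that way in isolation, but other sections place controls in the usual diabetes clinic. It is loose wording.

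It can also be said that the 41% is a ceiling and that the error rates rest on assumed correlations. Both points are right. What remains is the order of steps, the absence of described concealment, and the contradiction between sections.

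**Conclusion.** The point holds in this form. The operational sections assign patients on a pre-screened list to arms before invitation and written consent, and describe no concealment from the person who invites and consents them. The Lay Description and one Study Design bullet state the opposite order. Followed as written, the operational text permits selection by arm, which would touch every between-group comparison.

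The size cannot be fixed from the protocol. At most 147 of 359 (41%) could be lost after assignment, assuming the whole list is assigned. The bias and type I error figures show what could follow under assumed correlations and are not estimates for this trial. It would go too far to say that the groups are not randomised or that bias has occurred. The correction is nonetheless necessary, because it is cheap and the harm could not be removed afterwards.

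**What to change.** Amend Study Design, Randomisation and Seeking Consent to follow the order in the Lay Description:

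1. Confirm eligibility and take written consent.
2. Only then reveal the next allocation, from a computer-generated sequence held by an existing team member who does not recruit.
3. State in the telephone script that the type of care is decided by chance.
4. Reword the booking bullet so that each patient is booked into the clinic of the allocated arm.
5. If patients have already been pre-allocated, report the numbers invited, eligible and consented by arm.

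The sample size stays at 212, and these steps add no visits. The cost is a protocol amendment and someone to hold the sequence. Blocks stratified by BMI, or stopping at 212 in total instead of at 106 in each arm, are optional. A full common baseline before allocation is also not required for this fix. It might add an assessment step, because the protocol collects much of the baseline inside arm-specific clinics.

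### The operational sections assign listed candidates to arms before they are invited and consent, then fill each arm to 106 with no concealment described; this contradicts the stated consent-then-randomise order and lets entry depend on arm

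*Protocol*

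**What the plan says.** The protocol gives two orders of events.

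**Assignment before consent**

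- *Methodology, Randomisation.* The clinic database was reduced to a candidate list: "Once those that met the exclusion criteria were removed this list of potential participants (359) has been ranked from highest to lowest". Arm numbers come from an Excel random number generator, and "According to numbers allocated to the potential participant list these are then assigned to the two arms of the study (intervention and control". The timing is tied to ethics approval: "This will occur once ethic approval has been gained and prior to allocation to clinics". Consent comes in the following bullet: "Once case identified and consent gained participants will be recruited from pre-existing clinics".
- *Study Design.* Recruitment begins with the first 106 that the Excel program identifies for the two groups and "will continue until 106 participants have been recruited into both arms".
- *Informed Consent, Advertisement and Seeking Consent.* Candidates who have already been randomly selected get a notice with their next appointment. The Seeking Consent bullets run: list of records; eligibility screening by the Research Assistant; random allocation ("We will use a random number generator to assign patients to groups"); notice and invitation by the Research Assistant; written consent; booking into the next AMOS Clinic. No randomisation step stands between consent and booking.

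**Consent before assignment**

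- *Lay Description of Participation.* "They will be asked to provide written consent before being placed at random to the treatment group or normal care".
- *Summary* and the first bullets of *Study Design* can also be read as recruit first, then assign.

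**The concern.** Randomisation protects a comparison when nobody's entry can be influenced by the arm they will get. If the arm is attached to a name before the approach, willingness to join, or the effort spent on persuading someone to join, can differ by arm. Filling each arm to its own quota then replaces refusers from within that arm, and the final groups are two sets of consenters.

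The Research Assistant who screens, invites and takes consent is also the Case Manager, who under Resources ensures that participants receive their planned care. The protocol does not say who holds the sequence or how it is kept from this person.

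Both primary outcomes, HbA1c and body weight, plausibly depend on motivation. The adjustment set in the Analysis section (age, pre-existing diabetes, socio-economic status and ethnicity) does not measure it. The Rationale for Study Design chooses a randomised trial for its level of evidence, and that rests on allocation not influencing entry. The order of consent and allocation is fixed by the protocol, and an analysis plan cannot repair it afterwards.

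**Working it through.** **1. The plan's own sample size.** Inputs from the Sample Size section: d = 0.5, power 0.95, alpha 0.05 (two-sided assumed, since sidedness is not stated).

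n per arm = 2 × (1.960 + 1.645)² / 0.5² = 103.96, so 104. The t-test version gives 104.93, so 105. Both agree closely with the stated 106 per arm (212 in total). The number is sound, and nothing below changes it.

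**2. Uptake needed from the list.** 212 / 359 = 0.59. This is the minimum uptake that fills the trial from this list alone. It is not a forecast: higher uptake would fill the arms sooner, and people never approached because the arms are full are not selectively lost.

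**3. Illustration of bias (assumed values, not from the protocol).** Assumptions:

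- the true effect is zero;
- willingness to enter is standard normal, and one arm enrols the most willing fraction c of those approached;
- entry to the other arm is unrelated to willingness;
- willingness correlates r with the outcome.

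Mean willingness among enrolled people in the selected arm: m = φ(z) / c, where z is the normal quantile at 1 − c.

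- c = 0.59: m = 0.3886 / 0.5905 = 0.658
- c = 0.75: m = 0.3178 / 0.75 = 0.424
- c = 0.90: m = 0.1755 / 0.90 = 0.195

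Bias in SD units = r × m. The standard error of the difference with 106 per arm is √(2/106) = 0.137. The false-positive rate is the chance that a normal variable with mean bias / 0.137 and SD 1 falls outside ±1.96.

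| Uptake | r = 0.1 | r = 0.2 | r = 0.3 |
|---|---|---|---|
| 59% (minimum) | 0.07 SD; 8% | 0.13 SD; 16% | 0.20 SD; 30% |
| 75% | 0.04 SD; 6% | 0.08 SD; 9% | 0.13 SD; 15% |
| 90% | 0.02 SD; 5% | 0.04 SD; 6% | 0.06 SD; 7% |

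Against the planned effect of 0.5 SD, the 59% row is 0.066 / 0.5 = 13% to 0.197 / 0.5 = 39%.

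If everyone consents before a concealed assignment, the same selection acts on both arms and this source of bias is zero.

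**The case against.** The strongest reply is that the mechanism needs somebody to know the arm, and the protocol does not say that anyone does. The appointment notice and the telephone script are single texts for all candidates, and neither discloses an arm. Controls are described as wait-listed for the obesity clinic, which narrows any difference in incentive. No section says that the Research Assistant sees the arm list. The Seeking Consent bullets are also not strictly chronological, since the assistant's prior training is listed after the invitation. On this view it is a drafting inconsistency.

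Part of this stands: arm-dependent entry is possible and not shown. But the protocol provides nothing to prevent it, and two separate sections place assignment ahead of consent. The direct booking into AMOS after consent also fits that order better than the Lay Description.

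A reader might infer four stronger points, none of which the document supports:

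- *That arms are fixed before eligibility is checked.* The Randomisation section removes exclusions before numbering, and Seeking Consent lists screening before assignment.
- *That an arm could not fill if uptake fell below 59%.* This needs a closed list. The Timelines section plans ongoing recruitment, and the Sample Size section expects multiple intakes; neither confines later entrants to the 359.
- *That the comparison has already lost its randomised standing.* That would need evidence that entry did depend on arm.
- *That 8% to 30% is the expected false-positive rate.* It assumes minimum uptake, full selection in one arm and none in the other.

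**Conclusion.** The point holds as a contradiction with a real risk of bias. The Study Design, Randomisation and Informed Consent sections describe assigning candidates before invitation and consent and then filling each arm to 106; the Lay Description requires the reverse. With no concealment described, entry can depend on arm, and the planned covariates would not remove the result.

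The size cannot be derived from the document. Under the stated assumptions it runs from about 0.02 SD (90% uptake, correlation 0.1), which is negligible, to about 0.20 SD (59% uptake, correlation 0.3), the worst case. It needs correcting because it bears on both primary comparisons, cannot be undone in analysis and costs little to prevent.

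**What to change.** Apply the Lay Description's order throughout Study Design, Randomisation, Advertisement and Seeking Consent:

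1. Use the 359 only as an invitation list, and discard any arm numbers already drawn.
2. Confirm eligibility, obtain written consent and take baseline measures.
3. Then randomise each person 1:1 from a concealed sequence. An existing team member who does not screen, consent, treat or analyse should hold it. The lead academic would not qualify, because that role analyses the data. If blocks are used, vary their size and do not disclose it.
4. Stop at 212 randomised, analyse everyone randomised, and do not replace.
5. Insert the randomisation step between consent and clinic booking.

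Cost: a protocol amendment and a concealed allocation file. AMOS bookings cannot be made until each person has consented and been randomised. The sample size stays at 106 per arm, and no extra patients are needed.
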